4.2.1. Exclusion Criteria for SEEQ Heart Rhythm Monitoring Sub-study Only

- a) symptomatic arrhythmias for which heart rhythm monitoring is clinically indicated

4.3. Participant Recruitment and Screening

Participants at dialysis units affiliated with investigator and co-investigator practices will be screened for eligibility. In addition to active screening of dialysis unit patient rosters by study personnel, informational handouts and brochures may be disseminated at affiliated dialysis units in order to allow potential participants to learn about the study and to contact investigators if interested. All study material must be approved by local IRBs before dissemination to potential study participants.

Dialysis unit labs, medical records at the investigator's institution, and treatment or history records at local dialysis units will be reviewed to assess eligibility for enrollment. Prior to enrollment, each participant's treating nephrologist will be contacted to assess suitability for enrollment.

Once preliminary eligibility is confirmed, informed consent will be obtained by a qualified, investigator or study site designee during an in-person visit. This visit may take place either at

the local dialysis unit or at the investigator's institution (referred to hereafter as the Clinical Center), according to investigator and participant preferences. No study-specific testing is required to confirm eligibility, except a serum pregnancy test for women of childbearing potential (see **Section 4.3.1**), and serum potassium if a measurement is not available through clinical measurements within the specified time window. A Baseline/Randomization visit will be scheduled within 30 days of the screening visit.

4.3.1. Women of Childbearing Potential

Women of childbearing potential include any female who has experienced menarche and who has not undergone successful surgical sterilization (hysterectomy, bilateral tubal ligation, or bilateral oophorectomy) or is not postmenopausal. Postmenopausal is defined as:

- Amenorrhea for ≥ 12 consecutive months without another cause or
- Women with irregular menstrual periods and a documented serum follicle stimulating hormone (FSH) level > 35 mIU/mL or
- Women on hormone replacement therapy (HRT)

Women who are using oral contraceptives, other hormonal contraceptives (vaginal products, skin patches, or implanted or injectable products), or mechanical products such as an intrauterine device or barrier methods (diaphragm, condoms, spermicides) to prevent pregnancy, or who are practicing abstinence, or have a partner who is sterile (e.g., vasectomy) should be considered to be of childbearing potential.

Acceptable methods of highly effective birth control include:

- Condom with spermicide
- Diaphragm and spermicide
- Cervical cap and spermicide
- Hormonal contraception

4.4. Early Withdrawal of Participants and Early Termination of Study Medication

4.4.1. Early Withdrawal of Participants

Early withdrawals will be discouraged and participants who are not willing or able to continue study medication will be encouraged to remain in the study and continue study evaluations. In the case of withdrawal of consent, every attempt will be made to obtain consent to continue monitoring for the occurrence of mortality, hospitalizations and other safety signals via telephone or in-person contact with participants, relatives, and dialysis unit staff and records. As a last resort, the Social Security Death Index will be queried for mortality events on individuals otherwise lost to follow-up. If a patient becomes pregnant, she will be withdrawn from the study but will be followed for specific pregnancy outcomes.

4.4.2. Early Termination of Study Medication

Study medication will be discontinued by the research team in the following circumstances because of the potential for compromising patient safety:

- Allergy to or documented intolerance of study medications
- Poor adherence with dialysis schedule compromising ability to follow serum potassium on a monthly basis
- Organ transplantation
- Change to a different dialysis modality
- Initiation of digoxin therapy
- Transfer to a non-participating dialysis unit

If study medication is discontinued study visits and procedures will continue unless the participant withdraws consent for follow-up.

5. Study Drug

5.1. Description

Study drug will be administered as matched, gel-encapsulated capsules containing 12.5 mg, 25 mg or 50 mg of spironolactone (Spironolactone, 17-hydroxy-7 α -mercapto-3-oxo-17 α -pregn-4-ene-21-carboxylic acid γ -lactone acetate) or placebo (methylcellulose powder).

5.2. Treatment Regimen

As depicted in **Figure 1**, 125 participants will be randomized in a 2:1:1:1 fashion to either placebo or SPL (12.5, 25, or 50 mg), with an equal proportion in each SPL group. SPL will be matched with placebo and administered orally, once daily, post-dialysis. Participants will be instructed that, on days of dialysis treatment, the dose should be taken after the dialysis session. All patients will be started on SPL 12.5 mg once daily or matched placebo. Potassium levels will be checked 3-5 days and 2 weeks after initiation of study drug. Dialysis run-sheets will be evaluated weekly for the occurrence of adverse events such as hypotension and gastrointestinal symptoms. Adjustment to dosage of concomitant medications, the dialysis prescription, or study drug for hypotension or hyperkalemia will be made as described in **Section 6.8 and Section 6.9**.

At 2 weeks, in the absence of dose-limiting hyperkalemia or hypotension, subjects randomized to the 25 or 50 mg SPL arm will increase the dose to 25 mg and those randomized to 12.5 mg will continue that dose. At 4 weeks, in the absence of dose-limiting hyperkalemia or hypotension, participants randomized to 50 mg SPL will increase the dose to 50 mg SPL, and participants randomized to 12.5 mg or 25 mg will continue the same dose.

In order to maintain the blind, all study participants, regardless of randomized assignment, will receive a new study drug supply every 2 weeks during the dose escalation phase. For all participants, serum potassium levels will be checked at 3-5 days and at 2 weeks after the new study drug supply is dispensed, and weekly evaluations will be performed for tolerability, hypotension and hyperkalemia.

At the end of the dose escalation phase, participants will continue treatment based on the

randomized dose assignment for an additional 30 weeks (treatment phase) such that the total duration of study medication is 36 weeks. As described in **Sections 6.8 and 6.9**, the dose of SPL or placebo will be decreased or discontinued during the dose-escalation and treatment phases for hypotension, hyperkalemia or other dose limiting side-effects.

5.3. Method for Assigning Participants to Treatment Groups

The DCC will generate randomization schedules stratified by 1) participating recruitment site; 2) dialysis vintage (≥ 1 vs. < 1 year on dialysis) and 3) angiotensin converting enzyme inhibitor (ACEI) or angiotensin receptor blocker (ARB) use. Randomly permuted blocks of random sizes will be used to control the balance of participants assigned to each treatment regimen within each stratum. This method guarantees that at no time during randomization will the number of participants in any arm be grossly imbalanced, and ensures that the sites will be unable to predict assignments. Both longer dialysis vintage and use of ACEI or ARB increase the likelihood of hyperkalemia through loss of residual renal function and drug effects, respectively, and thus, are potential confounders that should be balanced across treatment groups.

All randomization schedules will remain confidential, and known only to authorized members of the DCC staff and the central pharmacy.

All relevant screening and eligibility confirmation data will be entered into the centralized data management system in advance of randomization in order for an eligible participant to be randomized. When the study team agrees that the patient should be randomized, and the "Ready to Randomize Report" confirms that all eligibility criteria have been met, the Study Coordinator will implement the web-based randomization assignment managed centrally at the DCC. This centralized randomization process will provide a randomized treatment assignment for that participant within the relevant stratum, linked with a specific study drug kit prepared at the central pharmacy. This kit will be provided to the local investigative team for distribution at the randomization/baseline visit.

5.4. Preparation and Administration of Study Drug and Maintenance of Blind

Study drug and matching placebo will be prepared by the University of Pennsylvania Investigational Drug Service (IDS) which will be the Central Pharmacy for this study. Study drug kits will contain 2-week supplies during the dose escalation phase, a 6-week supply for weeks 6-12, and 12-week supplies for weeks 13-24 and weeks 25-36.

Study drug will be prepared using gelatin encapsulation or equivalent methods such that all study drug, regardless of type (SPL or placebo) and dose are identical in appearance. During encapsulation, SPL tablets will remain intact and will not be altered. All dose levels will be administered as a single capsule. IDS personnel will have access to the randomization scheme and code in order to prepare study drug kits containing the correct dose of SPL or placebo. IDS personnel responsible for preparation of study drug will not have access to study data or results and will not participate in analyses of study data or publications. Randomized treatment assignments and the dosages provided in study drug kits will not be known by the Clinical Center research teams or the Clinical Center Research Pharmacy staff. Only the Investigational Drug Service personnel and the database programmer at the DCC will be unblinded.

During the 6-week dose escalation phase, a study drug request form signed by a Clinical Center investigator will be entered into the data management system at each 2-week interval to request the next supply of study drug. Unless there is a contraindication to a dose increase (e.g. hypotension or hyperkalemia), the investigator will indicate on the request form approval for dose escalation. The Data Management System will generate a unique kit number based on the randomized treatment assignment and the prior dose. If up-titration to the next dose is contraindicated, the Clinical Center investigator will indicate this on the study drug request form and a kit number corresponding to the current dose of SPL (or placebo) will be generated. At the end of the dose titration period, participants will be provided with a 6 week supply of study medication at the indicated dose. At the 12-week and 24-week visits, study drug request forms signed by the Clinical Center investigator will be submitted through the Data Management System to request 12 week supplies of study medication.

If down-titration of the study drug dose is required during the dose escalation phase or during the treatment phase, the Clinical Center investigator will request a dose reduction on the study drug request form. In this case, a supply of blinded study medication using the next lower dose of SPL (or placebo) will be provided. In the event that a participant is already receiving the lowest dose of SPL, placebo will be substituted for the first two down-titrations. As only 3 doses of SPL (12.5, 25 and 50 mg/day) are specified, study medication will be discontinued in the event that a 3rd down titration of dose is required (see **Table 1**). For participants already on placebo, a new supply of placebo will be provided in order to maintain blinding. Un-blinding to preserve patient safety will be considered via a formal request to the DCC.

If the dose escalation schedule is interrupted (e.g., if a participant is hospitalized at the scheduled time of dose escalation and did not take study drug during the hospitalization), dose escalation will be delayed until the participant has had access to the current dose of study drug for a total of two weeks. If, due to considerable delays in dose escalation, a participant has not reached the final dose assignment by their Week 12 visit, the participant will remain at the current dose of study drug for the remainder of the study and the treatment phase (i.e., the 30-week post-escalation period) will be shortened accordingly such that the total duration of study participation is not increased as a result of the delay. For example, if dose escalation is not completed until week 10, the treatment phase will be 26 weeks rather than 30 weeks.

Table 1. Study Drug Down-Titration Scheme

	Masked Study Drug	Masked Study Drug	Masked Study Drug	Masked Study Drug
Randomized Assignment	Placebo	12.5 mg	25 mg	50 mg
1st Down Titration	Placebo	Placebo	12.5 mg	25 mg
2nd Down Titration	Placebo	Placebo	Placebo	12.5 mg
3rd Down Titration	Discontinue	Discontinue	Discontinue	Discontinue

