3.1. General Design

This is a randomized, placebo-controlled 4-arm trial that will compare placebo with 3 doses of SPL. Participants will be randomized in a 2:1:1:1 fashion to placebo or SPL, with equal proportions randomized to each of 3 SPL doses: 12.5, 25 or 50 mg once daily. As shown in **Figure 1**, the study will be conducted in 2 phases – a dose escalation phase and a treatment phase.

All participants randomized to SPL will initiate treatment at 12.5 mg daily. Participants will be evaluated weekly for tolerability, hypotension and hyperkalemia. At 2 weeks, if the initial dose has been tolerated, participants randomized to the 25 or 50 mg SPL arm will increase the dose to 25 mg for 2 weeks with weekly evaluation for tolerability, hypotension and hyperkalemia. Participants randomized to 12.5 mg SPL or placebo arm will continue on the same dose with weekly evaluation for tolerability, hypotension and hyperkalemia.

[figure not shown]
At 4 weeks, participants randomized to the 50 mg SPL arm will increase the dose to 50 mg if the 25 mg dose was tolerated with weekly evaluations for tolerability, hypotension and hyperkalemia.

until 6 weeks. Participants randomized to 12.5 mg, 25 mg, or placebo will continue on the same dose with weekly evaluation for tolerability, hypotension and hyperkalemia until 6 weeks.

In order to maintain the blind, during the dose escalation phase all study participants, regardless of randomized assignment, will receive new study drug kits every 2 weeks and will be evaluated weekly.

At the end of the dose escalation phase, participants will continue treatment based on the randomized dose assignment for an additional 30 weeks (treatment phase) such that the total duration of study medication is 36 weeks. As described in **Sections 6.8 and 6.9**, the dose of SPL or placebo will be decreased during the dose-escalation and follow-up phases for hypotension, hyperkalemia or other dose limiting side-effects.

Figure 1. Study Design

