Blood will be obtained for measurement of serum potassium at 3-5 days and 2 weeks after the initiation of each new study drug kit during the dose escalation phase. Participants will be interviewed weekly in person or by telephone for the occurrence of serious adverse events and adverse events of interest. Adverse events of interest include hypotension, gastrointestinal symptoms, gynecomastia/breast tenderness, hyperkalemia and rash (see **Section 8.3.1**). Dialysis unit records will be reviewed for inter-current laboratory values, the occurrence of hypotension, and changes to the dialysis prescription. The dose of study drug may be reduced if a participant experiences dose-limiting adverse events, as outlined in **Section 6.8 and 6.9**.

A new supply of study drug will be dispensed and used pill containers returned at the week 2, week 4, and week 6 visits as described in sections **5.9.3 and 5.9.4**. Pill counts will be performed to assess participant adherence with study medication, and unused study drug will be destroyed by the Clinical Center research pharmacies once the pill count has been documented.

At the end of the dose escalation phase, participants in the heart rhythm monitoring sub-study will undergo heart rhythm monitoring using the Medtronic SEEQ device. The participant will wear the Medtronic SEEQ heart monitor for 7 consecutive days. Participants will receive the monitor kit from the research team and will return the kit after the monitoring period.

6.5. Week 8 (-4 to +3 days), Week 12, Week 16, Week 20, Week 24, Week 28, and Week 32 Visits (-7 to +7 days for all except Week 8)

Participants will be contacted at weeks 8, 12, 16, 20, 24, 28 and 32 either in person or by telephone to review the occurrence of serious adverse events and adverse events of interest as described in **Section 6.4**. Dialysis unit records will be reviewed for inter-current laboratory values, the occurrence of hypotension, and changes to the dialysis prescription. If a serum potassium value is not available in the participant's dialysis unit record, corresponding to the date of the monthly study visit (plus window), blood will be obtained from the participant for measurement of serum potassium. The dose of study drug will be reduced for participants experiencing dose-limiting adverse events as outlined in **Sections 6.8 and 6.9**.

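### The down-titration table in Section 5.4 is keyed to randomized assignment and contradicts the text's next-lower-dose rule for anyone reduced before reaching the assigned dose

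*Combined protocol and SAP*

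**What the plan says.** The relevant table is the Study Drug Down-Titration Scheme in Section 5.4. It is numbered Table 1, as is the unrelated table of hyperkalemia studies in Section 1.3.

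- **When reductions may happen.** Section 5.4 covers both phases: "If down-titration of the study drug dose is required during the dose escalation phase or during the treatment phase". Section 6.4, on the weekly visits in weeks 1 to 6, agrees: "The dose of study drug may be reduced if a participant experiences dose-limiting adverse events".
- **The rule in the text.** Section 5.4: "a supply of blinded study medication using the next lower dose of SPL (or placebo) will be provided". At the bottom of the range: "In the event that a participant is already receiving the lowest dose of SPL, placebo will be substituted for the first two down-titrations". A third reduction means discontinuation.
- **The rule in the table.** Columns are headed by randomized assignment. First and second steps are placebo then placebo for the placebo and 12.5 mg arms, 12.5 mg then placebo for the 25 mg arm, and 25 mg then 12.5 mg for the 50 mg arm. The third step is discontinuation throughout. No footnote restricts the table to participants already at the assigned dose.
- **Starting dose.** Section 3.1: "All participants randomized to SPL will initiate treatment at 12.5 mg daily". On schedule, the 25 mg arm reaches its dose at week 2 and the 50 mg arm at week 4.
- **Delay.** Under Section 5.4, escalation can be withheld or postponed. For someone not at the final dose by the week 12 visit, "the participant will remain at the current dose of study drug for the remainder of the study".
- **Kit selection.** In its paragraph on escalation requests, Section 5.4 says: "The Data Management System will generate a unique kit number based on the randomized treatment assignment and the prior dose".

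**The concern.** The text takes the dose in use as its starting point, and the table takes the dose assigned at randomization. The two agree only when those doses are the same. The escalation schedule makes them differ for every participant in the 25 and 50 mg arms for at least the first two weeks, and Section 5.4 expressly allows reductions in that period.

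A reduction is a response to hyperkalemia, hypotension or another dose-limiting effect. Potassium above 6.5 mEq/L and serious hypotension are the primary safety endpoints (Section 3.2.1). If the table were followed literally, a participant who needs less drug would get the same dose or a higher one. That participant would also be recorded as reduced, and so as a tolerability failure under Section 3.2.1, without having been reduced. Site teams and site pharmacies know neither the assignment nor the dose in the kit, so they could not see that the step had failed.

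**Working it through.** **Inputs.** The text rule, the table entries, the starting dose and the escalation times are those set out above. Section 7.1 plans 25 participants in each spironolactone arm, and Section 3.1 gives 36 weeks of treatment.

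**Step 1: reproduce the table.** Apply the text rule (50 to 25, 25 to 12.5, 12.5 to placebo, placebo to placebo, discontinue at the third reduction) from the assigned dose in each of the four arms. All 12 table entries are reproduced, so the table is correct for anyone at the assigned dose.

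**Step 2: apply the text rule from the dose being taken.** Escalation allows six arm-by-dose states among spironolactone participants.

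| Arm | Dose being taken | 1st reduction: table / text | 2nd reduction: table / text |
|---|---|---|---|
| 12.5 mg | 12.5 mg | placebo / placebo | placebo / placebo |
| 25 mg | 12.5 mg | **12.5 mg / placebo** | placebo / placebo |
| 25 mg | 25 mg | 12.5 mg / 12.5 mg | placebo / placebo |
| 50 mg | 12.5 mg | **25 mg / placebo** | **12.5 mg / placebo** |
| 50 mg | 25 mg | **25 mg / 12.5 mg** | **12.5 mg / placebo** |
| 50 mg | 50 mg | 25 mg / 25 mg | 12.5 mg / 12.5 mg |

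Conflicts are in bold. There are 3 in 6 states at the first reduction and 2 more at the second, so 5 of 6 × 2 = 12 state-by-step combinations. These are not 12 entries of the printed table. Only three printed entries are involved (25 mg arm first step; 50 mg arm first and second steps), and all three are right at the assigned dose. The third step always agrees.

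In all three below-assignment states the table's first step fails to reduce: twice the dose is unchanged, and once it goes from 12.5 to 25 mg.

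**Step 3: time at risk on the standard schedule.** The 25 mg arm is below assignment for 2 weeks and the 50 mg arm for 4 weeks:

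- Below assigned dose: 25 × 2 + 25 × 4 = 150 person-weeks.
- Planned in the two arms: 50 × 36 = 1,800 person-weeks.
- Share: 150 / 1,800 = 8.3%.

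**Step 4: expected number exposed.** The documents give no reduction rate. Assume a proportion p of the 50 participants needs a reduction, at a constant rate over 36 weeks. Expected exposed = p × 50 × 150 / 1,800.

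| p | Expected exposed |
|---|---|
| 5% | 0.05 × 50 × 0.0833 = 0.21 |
| 22% | 0.22 × 50 × 0.0833 = 0.92 |
| 50% | 0.50 × 50 × 0.0833 = 2.08 |

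The 22% is the average hyperkalemia incidence in the Section 7.1 power statement, used only as a stand-in.

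**Step 5: is a constant rate fair?** Potassium is checked more often early: twice per escalation kit (3 × 2 = 6 checks), then at weeks 8, 12, 16, 20, 24, 28, 32 and 36 (8 checks), 14 in all. Of these, 2 in the 25 mg arm and 4 in the 50 mg arm fall before the assigned dose is reached: (2 + 4) / 28 = 21%. This counts scheduled checks and does not forecast events, but it suggests detection may be more concentrated early than the 8.3% implies. Delayed or withheld escalation would also raise the exposure.

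**The case against.** The best defense is that the intended rule is not in doubt. The text speaks of the next lower dose and of what a participant is already receiving, so it refers to the dose in use. Its only pointer to the table is attached to the third-reduction rule, which never conflicts. The table then reads as a worked summary starting from the assigned dose. Kits requested during escalation draw on the prior dose as well as the assignment. Sites only request a reduction, so the possible misreaders are the database programmer and the central pharmacy, who would have to take a down-titration row as an order to repeat or double a dose. Section 6.9 adds safeguards: a recheck within one week at 6.0 mEq/L or above, and discontinuation at 7.0 or above. On this view a footnote is missing and nothing more.

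Much of this stands. The text does show the intent, reach is small, early monitoring would probably catch a failed reduction quickly, and nothing shows that a wrong kit would be issued. It does not remove the conflict. The kit sentence names the inputs to kit selection and sits in the paragraph on escalation requests; it does not say what a down-titration request returns. The only tabulated output is the table, and the people who program from it would find a different answer in the paragraph above. Nor is the discrepancy confined to escalation, because a participant can stay below the assigned dose to the end of the study.

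**Conclusion.** The concern holds: the table is wrong as written for participants below their assigned dose. The count of conflicts is exact and needs no assumption beyond reading the table literally. The placebo and 12.5 mg arms are unaffected, as is anyone at the assigned dose.

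The practical reach is limited. The estimate of about 0.2 to 2.1 participants depends on the assumed reduction proportion, a constant reduction rate and on-schedule escalation; early clustering or delay would raise it. Sample size, power and type I error are untouched. The documents do not show which rule the kit program follows, so this is a contradictory dosing instruction and not evidence of mis-dosing. It should be fixed because it concerns a safety action that blinded sites cannot verify.

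**What to change.** Either of two edits resolves it:

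1. Re-key the down-titration table to the dose being taken when the reduction is requested: 50 mg to 25 mg, 25 mg to 12.5 mg, 12.5 mg to placebo, placebo to placebo, and discontinue at the third reduction.
2. Keep the table and add a footnote that it applies only once the assigned dose has been reached, with the next-lower-dose rule in the text governing otherwise.

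In either case, have the unblinded programmer and the central pharmacy check the kit-assignment program against the chosen rule for all six arm-by-dose states.

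The cost is one table edit or footnote and six test cases. It adds no participants, visits or procedures.
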